### **6.5 Safety evaluation**

Serious adverse events will be presented in a descriptive way, showing the number and proportion with 95% Wilson confidence interval in each group.

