## 2. Study Methods

### 2.1 Trial design

The INTOMOB RCT is a multicenter, cluster, randomized, controlled, superiority trial conducted in three hospitals in Switzerland, with a 180-day follow-up. The intervention is partially blinded. Outcome assessment and data analysis are blinded. Hospital wards are randomized in a 1:1 ratio to either intervention or control arm. Patients admitted to an intervention ward receive the intervention, while patients admitted to a control ward receive standard of care.

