### 2.2 Randomization

Since the INTOMOB trial is a cluster RCT, only the wards (i.e., the clusters) have to be randomized. Ward randomization was done in a 1:1 ratio and generated shortly before start of the RCT by a statistician from CTU Bern (University of Bern, [name]). The statistician only received identifiers and not the actual names of the hospitals and wards in order to stay blind. Randomization was blocked with block size two and stratified by hospital to have the same ratio of intervention and control wards in each study center. Randomization was also stratified by ward size (<30 beds or  $\geq$ 30 beds). HCPs working on an intervention ward and participating patients admitted to an intervention ward receive the INTOMOB intervention. HCPs working on a control ward and participating patients admitted to a control ward receive the control procedure.

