### 2.3 Sample size

See section 5.1 of the protocol, under “Sample size calculation for the RCT”. The calculated sample size includes a total of 274 patients (137 in each arm, and in 12 clusters in total).

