## 4. Statistical Principles

### 4.1 Confidence intervals and *P* values

All effect measures will be accompanied by a two-sided 95% confidence interval. All applicable statistical tests will be two-sided and will be performed using a 5% significance level.

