## 6.2 Analysis methods

### 6.2.1 Primary analysis

The primary analysis will be an intention-to-treat analysis to compare the life-space assessment (LSA) between intervention and control groups at D30. LSA will be analyzed using GEEs with Gaussian distribution, exchangeable correlation structure and robust standard errors with small sample correction. This model accounts for the cluster design as well as for the small number of clusters and will be adjusted for the baseline LSA. The absolute difference between intervention group and control group will be presented with a 95% confidence interval (CI).

Continuous secondary outcomes will be evaluated likewise, adjusting for the baseline value if applicable. If outcome measures are non-normally distributed, we will apply an adequate distribution in GEE (e.g., gamma) or log-transform the outcome measure before analysis. Absolute differences between intervention group and control group will be presented with a 95% CI.

Binary outcomes will be analyzed using a GEE with a binomial distribution, a logit link, an exchangeable correlation structure and robust standard errors. Relative differences between groups will be presented as odds ratio with 95% CI.

Count outcomes will be analyzed using a GEE with a negative binomial distribution, a log link, an exchangeable correlation structure and robust standard errors. Relative differences between groups will be presented as rate ratio with 95% CI.

Time-to-event outcomes will be analyzed using a Cox regression model. To account for clustering, we will use shared frailties for clusters as well as cluster robust standard errors. Relative differences between groups will be presented as hazard ratio with 95% CI.

Categorical outcomes (discharge destination) will be analyzed using multinomial logistic regression with robust standard errors to account for clustering. Relative differences between groups will be presented as rate ratios with 95% CI.

Readmissions and emergency room visits will be analyzed as time-to-event outcomes, except if we notice that those outcomes often happen multiple times. In such case, we will analyze them as count outcomes.

Mortality and time to new institutionalization will be analyzed as time-to-event.

Falls will be analyzed as binary outcomes. If we notice that this outcome often happens multiple times, we will analyze it as a count outcome.

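### The SAE proportions get plain Wilson intervals that treat patients as independent although wards were randomised, so these intervals are too narrow if SAE risk varies between wards

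*SAP*

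**What the plan says.** **Design.** SAP section 2.1: "Hospital wards are randomized in a 1:1 ratio to either intervention or control arm". Section 2.2 confirms that "only the wards (i.e., the clusters) have to be randomized". Section 2.3 gives a total of 274 patients, "137 in each arm, and in 12 clusters in total".

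**Outcome models.** Section 6.2.1 says of the primary GEE: "This model accounts for the cluster design as well as for the small number of clusters". The other models in that section also allow for wards. Binary and count outcomes use GEEs with exchangeable correlation and robust standard errors. Time-to-event outcomes use Cox models with shared frailties and cluster-robust standard errors. Discharge destination uses multinomial regression with robust standard errors.

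**Safety.** Section 6.5: "Serious adverse events will be presented in a descriptive way", "showing the number and proportion with 95% Wilson confidence interval in each group". It mentions no design effect, robust variance or other allowance for wards.

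**The concern.** The Wilson interval is built on the binomial variance p(1 − p)/n, which is right for n independent patients. Patients on one ward share staff, case-mix and local practice, so their SAE outcomes may be correlated. The variance of an arm's proportion is then larger than binomial, and a nominal 95% interval covers less than 95%. The SAP recognises this correlation for its outcomes in section 6.2.1 but not for SAEs in section 6.5.

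Death shows the inconsistency. Table 2 takes it from the SAE form, and section 6.2.1 analyses it with allowance for wards. Counted as an SAE in section 6.5, the same event falls under an interval that ignores wards.

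At stake is how precisely the report claims to know the SAE risk in each arm of a trial meant to raise mobility in older inpatients.

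**Working it through.** **Inputs from the SAP.** 274 patients, 137 per arm, 12 wards, 1:1 allocation (sections 2.1 to 2.3); two-sided 95% intervals by the Wilson method (section 6.5).

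**Assumptions.** The SAP states none of the following:
- SAE proportion 20% (10% to 40% also tried), read as the proportion of patients with at least one SAE.
- ICC from 0 to 0.10.
- Ward sizes per arm 23, 23, 23, 23, 23, 22, and one unequal example of 40, 32, 25, 20, 12, 8.

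**The plan's own figure.** 2 × 137 = 274 agrees. The derivation of 274 is left to the protocol and cannot be reproduced here. Mean ward size is 274 / 12 = 22.8, with 12 / 2 = 6 wards per arm.

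**Step 1: design effect.** DEFF = 1 + ICC × (Σm² / Σm − 1). For the near-equal wards, Σm² = 5 × 529 + 484 = 3129, and 3129 / 137 − 1 = 21.84. At ICC 0.05, DEFF = 1 + 0.05 × 21.84 = 2.09 and the effective n is 137 / 2.09 ≈ 65.5.

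**Step 2: interval width.** Wilson limits are [p + z²/(2n) ± z√(p(1 − p)/n + z²/(4n²))] / (1 + z²/n), with z = 1.96. At p = 0.20 and n = 137 the limits are 14.2% and 27.5%. The adjusted limits put the effective n into the same formula.

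**Step 3: coverage.** Beta-binomial simulation, 100,000 replicates per setting, counting how often the plain Wilson interval on n = 137 contains the true proportion.

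Results at an assumed SAE proportion of 20%:

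| ICC | DEFF | Effective n | Adjusted interval | Width vs plain | Coverage of plain Wilson, near-equal wards | Same, unequal wards |
|---|---|---|---|---|---|---|
| 0 | 1.00 | 137 | 14.2% to 27.5% | 1.00 | 94.6% | 94.6% |
| 0.01 | 1.22 | 112 | 13.7% to 28.3% | 1.10 | 91.9% | 91.3% |
| 0.02 | 1.44 | 95 | 13.2% to 29.1% | 1.20 | 89.3% | 87.9% |
| 0.05 | 2.09 | 66 | 12.1% to 31.2% | 1.44 | 81.7% | 79.1% |
| 0.10 | 3.18 | 43 | 10.7% to 34.2% | 1.76 | 72.0% | 67.9% |

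The adjusted intervals and width ratios are for the near-equal wards.

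**Sensitivity to the SAE rate.** With near-equal wards and proportions of 10%, 30% and 40%, coverage is 93.1%, 92.4% and 93.1% at ICC 0.01, and 83.9%, 82.6% and 83.3% at ICC 0.05. The ICC drives the result; the SAE rate matters little over this range.

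**The case against.** **The display is descriptive.** Section 6.5 plans no test, effect measure or decision rule for SAEs. The rule in section 4.1, "All effect measures will be accompanied by a two-sided 95% confidence interval", concerns effect measures, and a proportion within one arm is not one, so section 6.5 does not breach it. This stands and limits the severity. It does not remove the point: a printed 95% interval still claims 95% coverage.

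**The interval might describe only the participating wards.** With the ward risks taken as fixed, plain Wilson does not under-cover (simulated 95.5% at 20% and ICC 0.05). But section 6.5 does not state that target, and the exchangeable GEEs and shared frailties of section 6.2.1 treat ward differences as a source of variation.

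**The size is assumed.** This stands. At ICC 0.01 the loss is about 3 points of coverage and 10% of width.

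**Stronger readings the SAP does not support.**
- A reader might infer that these are the only intervals on safety, or that harm can be judged only by comparing two short intervals. Table 2 lists death, falls, delirium, pressure ulcer, readmissions and emergency visits as outcomes, and section 6.2.1 gives each a ward-adjusted between-arm contrast. Only an overall SAE contrast is absent, which is a legitimate choice for a descriptive table.
- A reader might attach an inflated false-positive rate to the SAE comparison. An unadjusted two-arm z-test would reject in about 8% / 10% / 18% of trials at ICC 0.01 / 0.02 / 0.05 (assumed SAE proportion 30%), but the SAP plans no such test. Those figures also ignore the stratification by hospital in section 2.2, which balances hospital-level variation between arms. With two wards per hospital per arm (an assumed layout) and ICC 0.05, the rate falls from 17.6% to 11.6% if half the ward variance lies between hospitals, and to 7.2% if 80% does.

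**Conclusion.** The point holds for the SAE intervals. As specified, they ignore the ward correlation that the SAP allows for in its outcome models, and they are too narrow for any positive ICC. The loss runs from none at ICC 0, through a modest amount at 0.01, to a material one at 0.05.

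This rests on the assumed ICC and SAE rate, on about 6 wards per arm of roughly equal size, and on treating the wards as a sample from a wider set. More unequal ward sizes make the loss somewhat larger.

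Severity is minor to moderate, because no primary or secondary conclusion depends on these intervals.

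**What to change.** In section 6.5, say that the proportion is of patients with at least one SAE, and replace the plain Wilson interval by a ward-adjusted one that stays within 0 to 1 and suits few wards and low rates. Two candidates:
- Wilson on n / design effect, with the ICC estimated from the data and bounded below at 0.
- A cluster-robust interval on the logit scale, with small-sample correction and t quantiles.

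An untransformed ward-level t interval is not a safe substitute. At an SAE proportion of 30% it keeps about 95% coverage. At 5%, simulated coverage is 92% / 91% / 88% at ICC 0.01 / 0.02 / 0.05, and the lower limit is negative in 50% / 58% / 75% of runs.

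The alternative is to drop the intervals and report counts and proportions only. A ward-adjusted risk difference between arms is optional.

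**Cost.** A short SAP amendment that names the method, and a few lines of code, feasible before database lock. The intervals become wider. About six wards per arm estimate an ICC poorly: Wilson on the effective sample size keeps about 95% coverage when the ICC is known, and that figure should not be assumed when it is estimated.

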## **6.6 Subproject**

Not applicable.

## **6.7 Statistical software**

Stata version 18 (or higher) or R version 4.2 (or higher) will be used to carry out analyses.

## **6.8 Quality control**

A data analyst from CTU will perform a double programming of the primary analysis as well as a quality control of the final statistical report.

# **7. Changes from the Protocol**

The SAP is consistent with principle features of the statistical methods described in the protocol. Any deviation from the protocol is detailed hereunder with reason.

